This study will be the first to examine the feasibility and initial efficacy of a novel intervention using NRT preloading to improve smoking cessation outcomes in PWH. Given the high prevalence of smoking and the significant morbidity associated with it in PWH, the development of effective strategies to reduce the risks related to smoking in this group is critical. If determined to be effective, this intervention could be readily disseminated in HIV clinics. Our study will provide key information on the potential benefit of NRT preloading in a population that is highly dependent on nicotine and highly vulnerable to smoking-related morbidity and mortality. The results from this project will provide the foundation for a future R01 application to the National Cancer Institute to conduct a full-scale randomized clinical trial.

Aims

The specific aims of this randomized pilot study are:

Aim 1: To examine the feasibility and acceptability of NRT preloading in smokers with HIV. We will examine adherence (percent of days using the patch) to NRT prior to quit date in the preloading condition, and compare adherence after quit date across the standard (NRT-S) and preloading (NRT-P) conditions.

Aim 2: To examine differences in quit attempts and biochemically validated smoking abstinence between the

control and active conditions. We hypothesize that participants in NRT-P, compared to NRT-S, will have higher rates of CO-verified abstinence from smoking at weeks 8, 12 and 16. Cotinine verified abstinence at week 16.

Aim 3: To examine nicotine dependence, self-efficacy for cessation, and urge to smoke (craving) as mediators of abstinence. We hypothesize that participants in NRT-P, compared to NRT-S, will show greater reductions in dependence and urge to smoke, and greater increase in self-efficacy from baseline through quit date, and that these mediators will account for the effect of NRT-P on smoking abstinence at weeks 8 and 12 and 16.

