We will randomize 60 smokers with HIV to either NRT-P or NRT-S using urn randomization¹⁷ to ensure balance on gender and level of cigarette dependence (Fagerström Test of Cigarette Dependence (FTCD) score)¹⁸. Both

conditions will receive the same behavioral counseling support, which will be delivered in 5 sessions over 5 weeks, with the target quit date (TQD) scheduled at week 4. We will include 8 weeks of TNP for those in the ST condition (starting at TQD and continuing for 8 weeks) or 11 weeks of TNP for those in the NRT-P condition (starting 3 weeks prior to TQD). Dosage of TNP in each condition will be based on smoking rate and level of nicotine dependence at baseline (BL). All participants will also be provided with 8 weeks of nicotine lozenge or gum (started on TQD) and will be encouraged to use them every 1-2 hours to manage cravings and urge to smoke, with a goal of using at least 5 lozenges or gum daily. This instruction has been used in previous studies of this type and been shown to be beneficial^{19,20}. Smoking outcomes (7-day CO-verified point prevalence abstinence) will be assessed at 4, 8-, and 12-weeks after the TQD (Weeks 8, 12, and 16). Cigarettes per day, FTCD, urge to smoke, and self-efficacy for quitting will be collected at Baseline, and at 2- weeks after Baseline. We will compare NRT-P and NRT-S on adherence to pharmacotherapy (percent days using patch), smoking cessation rates, study retention and study satisfaction. We will calculate a preliminary effect size estimate of NRT-P on smoking and other secondary outcomes, and mechanisms of change. See Study Flow Diagram below.

Figure 1. Study Flow Diagram.

Recruitment and Participant Population

We will recruit participants (N=60) from the Providence community, the Miriam Immunology Center (MIC) in Providence, RI, and on social media (such as Facebook, Craigslist, Today@ Brown, Share lab website). Study information will be posted on the Share lab website at Brown. Study flyers will be posted on MIC bulletin boards, in the Providence community, and at AIDS-service organizations.

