Timeline Followback (TLFB) is a calendar-assisted structured interview designed to cue memory so that accurate recall is enhanced. The TLFB has established reliability and validity for smoking. The TLFB will be used to assess adherence to nicotine patch, all forms of tobacco use, marijuana use, and self-reported smoking for 7 days prior to baseline and week 2 visit, and for 7 days prior to each follow-up session at weeks 8, 12, and 16.

The Self-efficacy for Smoking Cessation Scale, which has shown good psychometric properties and excellent predictive validity, will be assessed at baseline, weeks 2, 4, 8, 12, and week 16.

Urge to smoke will be assessed at baseline and at weeks 2, 4, 8, 12, and 16 follow-up assessments using the Brief Questionnaire of Smoking Urges (B-QSU). This well-validated measure includes 10 items which assess urges to smoke for either positive reinforcement or negative reinforcement.

Biochemical Verification. All participants will provide breath samples for exhaled CO testing at baseline and at follow up sessions with the RA, at weeks 2, 4, 8, 12, and 16.

Other Measures

1. session attendance after baseline (continuous variable, range 1-6 study sessions);
2. retention (dichotomous variable, participants who complete the 16-week session with the RA will be characterized as completers, those not attending the final session as non-completers);
3. Smoking Situations Confidence scale, to measure self-efficacy for smoking cessation;
4. Readiness to Quit, using the Contemplation Ladder;
5. Treatment Satisfaction scale (CSQ-8).
6. Minnesota Nicotine Withdrawal Scale, to measure nicotine withdrawal symptoms. To be administered at weeks 4, 8, 12, and 16.
7. Commitment (to Quit) Scale, to be administered at baseline and week 4.
8. Quit Attempts (1-item) questionnaire, to measure quit attempts at weeks 4, 8, 12, and 16;
9. Anhedonia scale (3-item scale) at baseline, weeks 2, 4, 8, 12, and 16.
10. Medication Adherence Calendar, at weeks 4 (in active condition only), weeks 8 and 12.
11. Brief Qualitative Interview. An interview agenda will be utilized to explore perceptions of using psilocybin for smoking cessation in a future study. This is an opt-in procedure for current (at week 12 or week 16) and past study participants.

Analytic Plan.

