Treatment Feasibility, Acceptability, & Efficacy (Aims 1 and 2). We will first examine percent adherence to NRT prior to quit date in the NRT-P condition. We will then use t -tests to compare conditions on percent days adherent to NRT after TQD, and number of counseling sessions attended, and client satisfaction scores. We will compare side effects and NRT discontinuation rates between the active and control conditions. For treatment retention rate (dichotomous), a chi-square analysis will be used. Analyses of Aim 2 will test the hypothesis that NRT-P improves point prevalence abstinence relative to NRT-S. Tests of the effect of treatment condition on 7-day point-prevalence abstinence across the 8-, and 12-week assessments will be conducted using GEE, which provides appropriate modeling of covariance structures when observations are correlated across time⁸². The primary, between groups, independent variable in the GEE analysis is treatment condition assignment, which will be dummy-coded using NRT-S as the reference group. Following the intention-to-treat principle, all participants who have been randomized will be included in the analyses.

Potential Mechanisms of NRT-P Effects. Sample size in this pilot trial precludes formal mediation analysis with adequate power. The analyses are designed to test the plausibility of potential mechanisms of the NRT-P treatment effect. We will first run regression analyses predicting the putative mediators (nicotine dependence, self-efficacy for cessation, and urge to smoke) at both week 2 (1 week after those in NRT-P have initiated preloading) and week 4 (TQD) with treatment assignment and the BL value of the respective outcome as predictors. We will then enter change in the mediators from BL to week 2 and week 4 in the GEE models of smoking abstinence. Due to limited sample size, each mediator will be examined separately. We will examine

whether the effect of treatment is reduced when the mediator is added to the model and can test for significance (not expected given the sample size) using the products of coefficients method¹⁰⁵.

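### Aim 3: the abstinence GEE names change in each mediator but not its baseline value, so mediation is mis-sized if the level reached by quit date is what matters

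*Combined protocol and SAP*

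**What the plan says.** Under Potential Mechanisms of NRT-P Effects (Analytic Plan), dependence, self-efficacy and urge at week 2 and week 4 are each regressed "with treatment assignment and the BL value of the respective outcome as predictors". For the abstinence step: "We will then enter change in the mediators from BL to week 2 and week 4 in the GEE models of smoking abstinence". Mechanisms are judged by "whether the effect of treatment is reduced when the mediator is added to the model", and the plan adds that it "can test for significance (not expected given the sample size) using the products of coefficients method". It also concedes: "Sample size in this pilot trial precludes formal mediation analysis with adequate power".

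Aim 3 words the hypothesis as change: "greater reductions in dependence and urge to smoke, and greater increase in self-efficacy from baseline through quit date". Sex is the only covariate named for all analyses (Sample Size and Power Considerations). Study Methods makes FTCD an urn balancing factor together with gender, but the Aim 2 GEE text does not name FTCD.

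On timing, Study Methods says: "Cigarettes per day, FTCD, urge to smoke, and self-efficacy for quitting will be collected at Baseline, and at 2- weeks after Baseline". The measures section goes further for urge: "Urge to smoke will be assessed at baseline and at weeks 2, 4, 8, 12, and 16 follow-up assessments". It gives the same weeks for self-efficacy, but no such list for FTCD.

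**The concern.** The product of coefficients multiplies the effect of treatment on the mediator (the a-path) by the slope of abstinence on the mediator (the b-path). The a-path is conditioned on baseline. The b-path, as written, is not. Change from baseline is usually correlated with baseline within arm, so leaving baseline out makes the change slope absorb part of any effect that the starting level has.

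Randomisation and urn balancing do not remove this, because the issue lies in the within-arm relation of mediator to abstinence and not in imbalance between arms. At stake is whether a mechanism looks plausible in a pilot meant to support a full-scale trial application. A wrongly sized b-path is bias, and a larger sample would not remove it.

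**Working it through.** **Inputs.** From the documents: N = 60 (30 + 30, which agrees with 4 per month × 15 months), the two model statements, and sex as covariate. The documents give no mediator SDs, correlations, mediated share or power figure, so there is no stated figure to reproduce and every size below rests on assumptions.

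**Step 1: the a-path.** Let M0 be the baseline mediator, M1 the follow-up value, T treatment and D = M1 − M0. If M1 = α + aT + βM0 + e, then D = α + aT + (β − 1)M0 + e. The treatment coefficient a is the same, so the a-path is already a change-score model adjusted for baseline. The only mismatch is the unlisted baseline term in the b-path.

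**Step 2: the b-path.** Scale so that, within arm, Var(M0) = 1 and Var(M1) = k², with correlation r. Then Cov(M1, D) = k² − rk, Cov(M0, D) = rk − 1 and Var(D) = 1 + k² − 2rk. If abstinence depends on b1·M1 + b0·M0, the change-only slope (linear approximation) is

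[b1(k² − rk) + b0(rk − 1)] / (1 + k² − 2rk).

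- Change is the mechanism (b0 = −b1): the slope is b1, so there is no bias.
- Level is the mechanism (b0 = 0): the share recovered is (k² − rk)/(1 + k² − 2rk).
- Only baseline matters (b1 = 0): the slope is b0(rk − 1)/(1 + k² − 2rk). It points against mediation when rk < 1 and towards it when rk > 1.

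Share recovered under a level mechanism:

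| k | r = 0.4 | r = 0.6 | r = 0.8 |
|---|---|---|---|
| 0.85 | 0.37 | 0.30 | 0.12 |
| 1.00 | 0.50 | 0.50 | 0.50 |
| 1.15 | 0.61 | 0.67 | 0.83 |

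For example, k = 0.85, r = 0.8 gives (0.7225 − 0.68)/(1 + 0.7225 − 1.36) = 0.0425/0.3625 = 0.12. At rk = 1 (k = 1.25, r = 0.8) the share is 1. At k = 1.25, r = 0.9 it is 0.4375/0.3125 = 1.40, an overstatement. At k = 0.8, r = 0.9 it is −0.08/0.20 = −0.40, a reversed sign.

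If week-2 and week-4 changes enter one model together (equal SDs, r = 0.3 to 0.7), 33% to 67% of the week-4 indirect effect is recovered, depending on how much of it is already present at week 2.

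**Step 3: logistic check in a large sample.** Assumed: a = 0.5 SD, b = 0.8 and direct effect 0.2 (log-odds), r = 0.5, k = 1. Change-only against baseline added: slope 0.318 and 0.678 (ratio 0.47); product 0.159 and 0.339; fall in the treatment coefficient 32% and 63%.

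**Step 4: trials of 60.** Assumed: k = 1, r = 0.6, treatment shift −0.6 SD, conditional slope −1.1 per baseline SD, random-intercept SD 2.0, abstinence 28–33%. Models: three visits, exchangeable logit GEE, Mancl-DeRouen SE, 2,000 runs per case.

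| Mechanism and result | Change only | With baseline |
|---|---|---|
| Level: slope significant, hypothesised direction | 19% | 56% |
| Level: both product paths significant | 15% | 45% |
| Level: median product | 0.18 | 0.41 |
| Level: slope of wrong sign | 11% | 1% |
| Change: slope significant | 69% | 57% |
| Baseline only: significant, hypothesised direction | 0.1% | 1.5% |
| Baseline only: significant, opposite direction | 18% | 2.1% |

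With two visits (the Aim 2 analysis text names only 8 and 12 weeks) the first row is 17% and 51%. A repeat at the same k and r gave 18% and 53% for level, 70% and 56% for change, and a median drop in the treatment coefficient under a level mechanism of about 0.16 and 0.37. With only baseline mattering, k = 1.25 and r = 0.9, the median change-only slope was −0.27, which is in the hypothesised direction.

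**Step 5: FTCD in the Aim 2 GEE.** Eight assumed settings, 3,000 runs each. Adding FTCD moved power from 30–42% to 39–45% under an assumed large effect. The SE did not fall; the odds ratio moved from 2.12–2.37 to 2.42–2.47. Type I error with a plain robust SE went from 3.1–4.8% to 4.9–6.6%; with the corrected SE it was 2.0–3.4% without FTCD and 3.0–3.8% with it. The simulated balance was tighter than an urn gives, so the gain is an upper bound.

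**The case against.** The strongest reply is that the plan analyses what it hypothesises. Aim 3 predicts change through quit date, and change is what enters the GEE. No section posits a level mechanism. If change is the mechanism, adding baseline only costs precision. That stands, and it is why change-only should be kept as a reported analysis. But no section says that starting level is irrelevant to abstinence, and change plus baseline is unbiased under either mechanism.

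The plan also gives no full covariate list, so a baseline term may be intended. That stands too; one sentence would settle it.

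The simulated effects are large, while the plan does not anticipate large effects. With a slope of −0.55 and a 0.3 SD shift, detection is 7% against 14%; with a slope of −0.3 it is 2% against 5%. A mixed mechanism (baseline coefficient half the size, opposite sign) gives 40% against 54%. The absolute loss in detection can therefore be small, although the share recovered does not depend on the size of the effect.

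A reader might infer that the two paths are incompatible and the product meaningless. Step 1 shows otherwise. A reader might also infer that change-only always understates mediation and never lends it false support. That fails when rk > 1.

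**Conclusion.** The point holds conditionally and is minor. If the level reached by quit date drives abstinence, change-only recovers about half the slope and product at equal SDs and 12–83% over the grid shown, with overstatement once rk exceeds 1. The drop in the treatment coefficient is affected as well, so both of the plan's criteria are touched. If change drives abstinence, the plan as written is right and somewhat more precise.

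The values of k, r, shift and slope are all assumptions, the share formula is a linear approximation, and logit coefficients are not collapsible, so coefficient drops are approximate in either model. The plan itself presents the step as an unpowered plausibility check. Leaving out the mediator's baseline value does not bias the Aim 2 treatment comparison; naming FTCD there is a separate, modest improvement.

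A reader might infer that dependence cannot be analysed at week 4 because FTCD is not collected then. The documents do not establish that. The Study Methods list also omits week 4 for urge and self-efficacy, which are collected then; Description and Purpose says that dependence is examined before and after quit date; and the Schedule of Assessments that the protocol refers to is not in the text provided.

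**What to change.** 1. In each mediator GEE, and in the matching model without the mediator, include that mediator's baseline value beside its change score. Fit week 2 and week 4 in separate models. Report the change-only model as a sensitivity analysis. Cost: wording and one degree of freedom per model, with no new data. If change is the mechanism, detection falls from about 70% to 56% under the assumptions above. If only baseline matters (k = 1, r = 0.6), false positives in the hypothesised direction rise from 0.1% to 1.5%, still below the nominal 2.5%.
2. Include baseline FTCD beside sex in the Aim 2 GEE, with a small-sample-corrected robust SE, and also report the odds ratio without FTCD, because the adjusted one is a different quantity. The gain is modest. For the dependence mediator, items 1 and 2 add the same variable, which enters once.
3. As a clarification only, reconcile the FTCD timing in Study Methods (baseline and 2 weeks) with the week-4 dependence analysis: state that FTCD is collected at week 4, or limit that analysis to week 2. The Schedule of Assessments may already settle this.

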TITLE: Preloading with Nicotine Replacement Therapy in Smokers with HIV to Improve Self-Efficacy and Quit Attempts

NCT04994444

V.2. 08/12/2021

Project Title: Preloading with Nicotine Replacement Therapy in People with HIV who Smoke to Improve Self-Efficacy and Quit Attempts

Principal Investigator:

[name]

Co-Investigator:

[name]

Description and Purpose of the Project

Cigarette smoking is more prevalent in persons with HIV (PWH) in the U.S. when compared with the general population and is linked to increased morbidity and mortality in this population. Furthermore, PWH who smoke have increased rates of lung and other smoking-related cancers. PWH who smoke are a particularly challenging group, often reporting high severity of nicotine dependence and low rates of self-efficacy for quitting, both factors related to poor smoking cessation outcomes. Establishing more effective smoking cessation approaches for people with HIV who smoke, particularly those that address low self-efficacy and severe dependence, is a public health priority.

The overall goal of this research project is to examine the feasibility, acceptability, and preliminary efficacy of nicotine replacement therapy preloading (NRT-P) in PWH who smoke, who are struggling with cigarette dependence, urge to smoke (craving) and low self-efficacy as barriers to successful smoking cessation. Sixty participants will be recruited into a 16-week randomized pilot study. Thirty participants (control condition) will receive standard smoking cessation counseling (NRT-S) and will initiate an 8-week course of combination nicotine patch and lozenge (or gum, based on preference) on quit date (week 4), consistent with recommended guidelines based on smoking rate. Thirty participants (active condition) will start NRT patch 3 weeks prior to quit date, followed by an 8-week course of combination nicotine patch and lozenge (or gum, based on preference), initiated on quit date. We will examine dependence, urge to smoke and self-efficacy for quitting prior to and following quit date. We will also examine differences in quit attempts and biochemically validated smoking abstinence between the control and active conditions at weeks 8, 12, and 16.

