Assessments will be designed as Qualtrics surveys and paper surveys. Qualtrics will be used for all data collection. If Qualtrics is unavailable, the RA may use paper surveys for data collection. The data will then be transferred into Qualtrics. Data will be verified, checked, and uploaded to an SPSS file to conduct analyses. Initial data analysis will include distribution properties of baseline variables, and correlations among outcome measures.

Data Analysis. Initial data analysis will include examination of BL characteristics by condition, distribution properties of dependent and other variables, patterns of missing data by condition and correlations among outcome measures. **Sample Size and Power Considerations.** Our primary objective will be to examine preliminary effect sizes for NRT-P, rather than to determine statistical significance between groups at certain p values. At the same time, we are well aware of the dangers of relying exclusively on small-scale pilots to determine the promise of novel treatment approaches¹⁰¹. These effect size estimates have a large standard error, and we primarily will be hoping to find a pattern of results that is supportive of the experimental treatment. Effect size estimates will include odds ratios for smoking abstinence. We believe a sample size of 60 should allow adequate examination of NRT-P intervention effect sizes while staying within the scope of a developmental project. We recognize that only large effect sizes will be likely to attain statistical significance with a sample of this size, and large effect size are not anticipated. Our data also will allow us to obtain stability estimates for point-prevalence abstinence (i.e., intercorrelations among outcomes at 4 and 12 weeks). Using a program that allows us to specify proportions at each time point and the correlations between time points¹⁰², we will be able to get a good estimate of the sample size needed to find a significant main effect of treatment in a repeated measures analysis using generalized estimating equations^{103,104}. All analyses will include sex as a covariate, and follow-up analyses will test the Sex x Condition interaction to determine whether sex moderates the effects.

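### Aim 3 takes shrinkage of the treatment odds ratio as evidence of mediation, but on a logit scale that comparison understates mediation and can sometimes show none

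*Combined protocol and SAP*

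**What the plan says.** Aim 3 hypothesises that "these mediators will account for the effect of NRT-P on smoking abstinence at weeks 8 and 12 and 16". The method is in the Analytic Plan under Potential Mechanisms of NRT-P Effects and has three steps.

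1. Each mediator (dependence, self-efficacy, urge to smoke) at weeks 2 and 4 is regressed "with treatment assignment and the BL value of the respective outcome as predictors". This is the a-path, from treatment to mediator.
2. "We will then enter change in the mediators from BL to week 2 and week 4 in the GEE models of smoking abstinence", one mediator at a time.
3. The analyst looks at "whether the effect of treatment is reduced when the mediator is added to the model". As an option, the same sentence adds that the analyst "can test for significance (not expected given the sample size) using the products of coefficients method".

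The outcome is binary, 7-day point-prevalence abstinence. The link function is not named. Under Sample Size and Power Considerations the plan says "Effect size estimates will include odds ratios for smoking abstinence", from which a logit link is inferred here. The plan is modest about this analysis: "Sample size in this pilot trial precludes formal mediation analysis with adequate power". It does not mention rescaling, a risk-difference contrast or an interval for the indirect effect.

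**The concern.** Log odds ratios are not collapsible. The treatment coefficient from a logit model changes when a predictor of the outcome is added, even if treatment does not affect that predictor. With a non-zero direct effect the change is away from zero. The criterion looks for movement towards zero, so two opposing movements are mixed: shrinkage from mediation and inflation from the change of scale. The shrinkage that remains is smaller than the true mediated share, and when the mediator predicts abstinence strongly but treatment moves it only a little, the sign can reverse.

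The plan does not expect significance, so this descriptive check carries much of the Aim 3 reading. The pilot is meant to support a full-scale trial application, and a genuine mechanism could be played down because of the scale.

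**Working it through.** **Inputs from the documents.** Binary abstinence, odds ratios, mediators examined singly, 60 participants (30 per arm). The documents give no abstinence rate, effect size or mediator strength, and no mediation figure to reproduce, so those inputs are assumptions.

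**Model.** Let T be treatment and M the mediator change in SD units, with M = a·T + Z and Z standard normal. Let logit P(abstinent) = b0 + c′·T + b·M. Averaging over Z gives p(t, m) = E[expit(b0 + c′·t + b·(m + Z))], and b0 is set so that p(0, 0) = 0.20. Then:

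- coefficient with the mediator: c′
- coefficient without it: c = logit p(1, a) − logit p(0, 0)
- reduction the plan would see: 1 − c′/c
- true share, log-odds scale: [logit p(1, a) − logit p(1, 0)] / c
- true share, risk scale: [p(1, a) − p(1, 0)] / [p(1, a) − p(0, 0)]
- product-of-coefficients share: ab / (ab + c′)

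**Results with b = 1.0 per SD (b0 = −1.650).**

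| a | c′ | p(1, 0) | p(1, a) | c | OR without → with mediator | Reduction seen | True share, log-odds | True share, risk | Product share |
|---|---|---|---|---|---|---|---|---|---|
| 0 | 0.693 | 0.3110 | 0.3110 | 0.591 | 1.81 → 2.00 | −17% | 0% | 0% | 0% |
| 0.1 | 0.693 | 0.3110 | 0.3293 | 0.675 | 1.96 → 2.00 | −3% | 12% | 14% | 12.6% |
| 0.3 | 0.693 | 0.3110 | 0.3672 | 0.842 | 2.32 → 2.00 | 18% | 30% | 34% | 30.2% |
| 0.2 | 0.400 | 0.2606 | 0.2945 | 0.513 | 1.67 → 1.49 | 22% | 33% | 36% | 33.3% |

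Last row written out: c = logit(0.2945) − logit(0.2000) = −0.874 + 1.386 = 0.513. Reduction seen = 1 − 0.400/0.513 = 22%. True log-odds share = [−0.874 − (−1.043)] / 0.513 = 33%. Product share = 0.2/(0.2 + 0.4) = 33.3%.

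The like-for-like comparison is with the log-odds share. The risk-scale share differs partly because it is a different scale.

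**Where the bias is small.**

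- Control abstinence 10%, direct odds ratio 1.5, b = 0.5 to 0.7, a = 0.2 to 0.3: the reduction is 2 to 4 points below the true log-odds share (for example 17.5% against 19.7%, and 30.3% against 33.9%).
- Direct effect near zero (20% abstinence, b = 1.0, a = 0.3, c′ = 0.01): 96.2% against 96.8%.

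**Where it is large** (total odds ratio 2.0, a = 0.3, control abstinence 10 to 30%): 8 to 14 points for a mediator odds ratio of 3 per SD, and 14 to 23 points for 5 per SD. With 20% abstinence, mediator odds ratio 3 and a = 0.1, the coefficient grows (−5.0%) although the true share is 12.9%.

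**Against sampling noise.** Simulated trials of 60 participants with three correlated visits (20% control abstinence, a = 0.3, total odds ratio 2.0; 3,000 replicates per scenario):

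| Mediator OR per SD | c − c′ | ab | Gap | SD of c − c′ | No reduction seen | Product ≤ 0 |
|---|---|---|---|---|---|---|
| 2 | 0.147 | 0.208 | 0.061 | 0.21 | 20% | 13% |
| 3 | 0.185 | 0.330 | 0.145 | 0.31 | 25% | 12% |

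The gap is well below one SD. Even so, the reduction check missed real mediation 7 to 13 percentage points more often than the sign of the product did.

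**The case against.** The strongest reply is that the plan already holds most of the remedy. The product-of-coefficients method is named in the same sentence, does not compare coefficients across models, and tracks the true log-odds share closely. The a-path regression is planned, and the b-path comes from the GEE that contains the mediator. This much stands. A reader might infer that the reduction check is the plan's only evidence on mechanism, or that a strong predictor treatment does not move would be taken for a suppressor. The documents do not support either: the first-stage regression would show no treatment effect on such a predictor, apart from sampling error. But the product is optional and offered only for a significance test that the plan expects to fail, so it limits the problem without removing it.

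A second reply is that the analysis is declared a plausibility check, sets no threshold for the share mediated, and is dominated by noise at this size. That lowers the stakes. It does not justify a measure with a known directional bias when a better one comes from the same models. Non-collapsibility should not, however, be blamed for everything that can go wrong: a total effect estimated at zero or below, which leaves the reduction without meaning, is ordinary pilot sampling error.

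Third, the net direction of error is uncertain. Mediator change is not randomised, and common causes of mediator and abstinence could produce apparent mediation. That is a separate bias and cannot be relied on to cancel this one.

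**Conclusion.** The point holds as a descriptive bias that should be corrected. If the GEE uses a logit link and treatment has a non-zero direct effect, the reduction criterion understates mediation. At 20% control abstinence and a mediator log odds ratio of 1.0 per SD, the shortfall is about 11 to 15 points of log-odds share in the scenarios above (33% seen as 22%, 30% as 18%, 12% as −3%). It is a few points for weak to moderate mediators or low abstinence, and nil as the direct effect goes to zero.

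A reader might go further and conclude that the plan hides mediation, or misreads Aim 3 at any sample size. The documents do not support that. Reversal needs a strong mediator together with a small treatment-to-mediator effect or a large direct effect, and the plan gives no figures that would place the trial there. The sizes rest on assumed abstinence rates, effect sizes and mediator strengths, a normally distributed mediator with no unmeasured confounding, and an inferred link.

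**What to change.** Under Potential Mechanisms of NRT-P Effects:

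- Name the link function of the abstinence GEE.
- Replace the reduction criterion. For each mediator report the a-path (already planned), the b-path, and the indirect effect as the main summary. The indirect effect can be the product of coefficients, or a risk difference predicted from the fitted GEE with the mediator at its NRT-P and then its NRT-S level and treatment held fixed.
- Give a 95% interval from a bootstrap that resamples participants, so that repeated visits stay together.
- If a with/without comparison is kept, put both models on a common scale (risk difference or rescaled logits) and fit them on the same participants. Otherwise those lost to follow-up, counted as smoking, stay in the model without the mediator and drop out of the other when their mediator change is missing.
- State that unmeasured common causes of mediator and abstinence could bias the indirect effect in either direction.

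Cost: SAP wording and a short script. No new data or visits. The intervals will be wide with 60 participants, which fits the plan's own statement about power.
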